13. STRUCTURED RISK ANALYSIS
14. REFERENCES

## **LIST OF ABBREVIATIONS AND RELEVANT DEFINITIONS**

CRP	C-reactive Protein
GA	Gestational Age
GP	Glycoprotein
HPA	Human Platelet Antigen
IC	Informed Consent
ICH	Intracranial Haemorrhage
IvIG	Intravenous Immunoglobulin
FNAIT	Fetal and Neonatal Alloimmune Thrombocytopenia
Rhc	Rhesus c
RhD	Rhesus D
RIVM	National Institute of Public Health and the Environment (in Dutch: Rijksinstituut voor Volksgezondheid en Milieu)

## **SUMMARY**

**Rationale:** Fetal and Neonatal Alloimmune Thrombocytopenia (FNAIT) is the most common cause of severe thrombocytopenia in neonates. It is an immunological process, in which Human Platelet Antigen (HPA) alloantibodies produced by the mother can cross the placenta and target fetal platelets. The most frequent alloantigen to elicit platelet-reactive antibody responses is HPA-1a. The resulting low platelet count in the fetus or neonate correlates with an increased risk of bleeding complications and severe adverse outcome, defined as perinatal death or intracranial haemorrhage (ICH). This can lead to life-long handicaps, cerebral palsy, cortical blindness and mental retardation. One in 50 pregnancies is at risk for FNAIT, since 2,1% of the Caucasian population is HPA-1a negative. Alloantibodies are calculated to be present in 1:400 pregnancies, leading to FNAIT-related severe adverse outcome in at least 1:1300 fetuses or neonates, and this is likely an underestimation. There is a highly effective antenatal treatment available for preventing these severe adverse outcomes, consisting of weekly injection of intravenous immunoglobulins (IvIG). Unfortunately, in the current state of practice, this treatment can only be given in subsequent pregnancies because the disease is diagnosed after birth of a symptomatic child. In the presence of an antenatal screening program for HPA-alloantibodies all pregnancies at risk can be identified in time, to start IvIG treatment and reduce severe adverse outcomes. However, before such a program can be realised detailed information about incidence and natural course of the disease is needed. Furthermore laboratory tests are needed to identify fetuses at high risk to prevent overtreatment, since approximately 10-30% of the HPA alloimmunised cases result in severe thrombocytopenia and clinically relevant disease.

### **Objectives:**

1. The main objective of this study is to assess the incidence and severity of FNAIT and bleeding complications (including ICH) among neonates.
2. To develop a screening platform, including diagnostic assay(s) to identify fetuses at high risk for bleeding complications due to FNAIT.

**Study design:** Prospective observational cohort

**Study population:** Pregnant women

**Main study parameters/endpoints:** The main study parameters are HPA-1a alloantibodies, clinically relevant FNAIT. Secondary parameters include: neonatal outcome (bleeding signs other than ICH, treatment for thrombocytopenia, morbidity).

**Nature and extent of the burden and risks associated with participation, benefit and group relatedness:** These pregnant women participate in the national antenatal screening programme for Prevention and Screening of Infectious diseases and Erythrocyte Immunisation (PSIE) and have a routine blood sampling at 27th week of gestation. We will use this blood sample to perform all necessary tests, so no additional (medical) procedures will be performed. Additionally, after delivery we collect clinical data concerning the pregnancy, delivery and the health of the child in the first postnatal period by means of questioning the obstetric health care provider.

## 1. INTRODUCTION AND RATIONALE

Fetal and Neonatal Alloimmune Thrombocytopenia (FNAIT) is the most common cause of severe thrombocytopenia in neonates. In pregnancies complicated by FNAIT, Human Platelet Antigen (HPA) incompatibility between mother and fetus can lead to production of alloantibodies. In Caucasians, the most frequent alloantigen to elicit platelet-reactive antibody responses is the HPA-1a.[1] These antibodies can cross the placenta and lead to destruction of fetal platelets causing FNAIT. Consequently, this can cause bleeding complications in fetus and neonates, of which the most severe complication is intracranial haemorrhage (ICH), leading to perinatal mortality in 7%-10% and severe neurological sequelae including mental retardation, cerebral palsy and cortical blindness 10-20% of FNAIT pregnancies.[2-4]

In the Netherlands, an estimated one in 50 pregnancies is at risk for FNAIT, since 2,1% of the Caucasian population is HPA-1a negative.[5] Alloimmunisation occurs in approximately 12% of these cases, with development of severe fetal thrombocytopenia (platelet count < 50x10^9/L) occurring in about 150 cases each year. This leads to severe adverse outcomes in 20-25 pregnancies, with approximately 13-17 children born with an ICH each year, who are at serious risk for life-long neurodevelopmental handicaps, and this is likely to be an underestimation.[1] The disease has close similarities to haemolytic disease of the fetus or newborn due to red cell (mainly Rh) alloimmunisation in pregnancy, for which all western countries have implemented screening programs to start timely treatment. Screening for FNAIT has an international interest. Recently, the National Institute of Public Health and the Environment in the Netherlands (in Dutch: Rijksinstituut voor Volksgezondheid en Milieu; RIVM) recognised FNAIT as a significant disease, and advised to obtain more knowledge on detection and treatment of screen-detected FNAIT-risk cases, to support possible national implementation of screening. Results from a large prospective screening study in Norway amongst 100,000 pregnant women, suggest that screening all pregnant women for FNAIT could significantly reduce adverse outcome and might be cost-effective.[6, 7] Their interventions however, were restricted to offering a near-term caesarean section and availability of matched platelets at birth. As expected, their policy did not prevent several cases of neonates born with ICH of antenatal origin. We hypothesise that a further reduction of this serious adverse outcome might be possible by providing antenatal treatment in the screen-positive pregnancies.

In the last decade, our insights in the pathophysiology, laboratory methods for detection of pregnancies at risk and treatment options have vastly increased. Until now, affected fetuses and neonates are only diagnosed in the presence of, invariably totally unexpected, clinical symptoms, when treatment is often too late. In a subsequent pregnancy the current management consists of offering non-invasive preventive measures including maternal administration of intravenous immunoglobulin (IvIG). Research from our group suggests that antenatal treatment of the mother with IvIG is highly effective in the prevention of FNAIT related ICH.[8] It is likely that in presence of an antenatal screening and intervention program, perinatal death and severe handicap due to FNAIT can be significantly reduced in our country. To realise such a screening program adequate information about the incidence and prevalence of both the HPA-1a alloimmunised pregnant population and the subset of cases showing clinically relevant disease is necessary. This information is not retrievable from publications, because these involve a selected population or provide antenatal treatment.

Calculations suggest that screening pregnant women for HPA antibodies, and start IvIG treatment for those is cost-effective.[6] However, since in approximately 10-30% of the alloimmunised cases a severe thrombocytopenia is found and the antibody titres alone do not seem to correlate with the severity of the disease, a screening program using current methods might result in unnecessary anxiety and “over-treatment” in the screen positive cases.[9, 10] Therefore further laboratory tests to identify fetuses at high risk need to be defined. In this light we recently found that HPA-1a alloantibody characteristics such as a low Fc-glycosylation correlate with disease severity.[11] Furthermore, we have demonstrated that HPA1a

alloantibodies induce heterogeneous levels of e.g. phagocytosis of HPA-1a opsonized platelets, reduction of integrity of endothelial cell layers and platelet aggregation; the clinical relevance, in terms of thrombocytopenia and bleeding tendency, of these observations needs to be further confirmed.

This protocol describes the outline and background of a prospective study providing information about the natural course of this disease necessary to ultimately develop a nationwide screening program. Furthermore it enables us to further validate several assays, which could be used to further analyse the characteristics of the screen-detected cases.

## **2. OBJECTIVES**

### Primary Objectives:

- To assess the incidence of HPA-1a alloantibodies and the incidence of clinically relevant FNAIT in the Netherlands.

[figure not shown]
### Secondary Objective(s):

- To develop a screening platform, including diagnostic assay(s) to identify fetuses at high risk.
- To determine the number of pregnant women whose children would benefit from treatment and the number who will receive treatment unnecessarily.
- To assess costs and effectiveness of implementing a nationwide screening program for FNAIT.

### 3. STUDY DESIGN

We will perform an observational prospective cohort study, during a period of two years. All pregnant women, participating in the nationwide prevention program organized by the RIVM to screen for red cell alloimmunisation in Rhesus D (RhD) and Rhesus c (Rhc) negative pregnant women, will be informed about participation in our study. The RIVM was consulted during the development of the study design and consented under certain conditions. An informed consent procedure will be applied, in which the RhD and Rhc negative pregnant women will be informed by their obstetric caregivers using our information flyers and are subsequently given the opportunity to either accept or object to participation. See chapter 11.2 for further specification. Regardless, all blood samples of RhD and Rhc negative pregnant women will be tested, because the blood sample for HPA-1a typing is needed to be fresh. These data will be quarantined. The HPA-1a typing will be performed using the blood sample that is already send to Sanquin.

Figure 1 - Flow chart of study design

Nothing will be changed about the procedure as it currently is, regarding to the logistics as well as the volume of blood drawing itself. Blood samples from the expected 2.1% HPA-1a negative women and a control group consisting of 3 random HPA-1a positive women for each HPA-1a negative woman will be stored.

When receiving an objection to participate these samples will be deleted from storage as well from the database. After delivery, the stored blood sample will be used to test for the presence of HPA-1a alloantibodies. Clinical follow up data concerning the first postnatal period will be obtained by directly contacting the obstetric and paediatric care givers. After obtaining clinical information the depicted samples can be used to determine the diagnostic accuracy of several experimental assays that may be used to discriminate high risk cases, who will develop clinically relevant disease, from low-risk cases. An overview of the study design is displayed in **Figure 1**.

[figure not shown]
**4. STUDY POPULATION**

*4.1 Population (base)*  
Pregnant women.

*4.2 Inclusion criteria*  
All pregnant women, of whom routine blood samples are taken at 27 weeks gestational age (GA).

*4.3 Exclusion criteria*  
There are no predefined exclusion criteria, since we are aiming to determine the incidence in the complete pregnant population in the Netherlands.

*4.4 Sample size calculation*  
Approximately 2.1% of pregnant women are HPA-1a negative, thus 1:50 pregnancies.[1, 12] In about 12% of these women HPA-1a alloimmunisation will occur and in circa one third of these cases this will cause severe FNAIT (platelet count <50 x10^9/l), of which 10% will be suffering from ICH, or 1:12.500 pregnancies.[1] In the Netherlands we thus expect a minimum of 16 affected children annually, who could possibly suffer life-long handicaps and neurological damage.

*\* based on an enrolment of 80%, for a study period of 2 years*

Each year there are approximately 60.000 RhD and/or Rhc negative pregnant women, to be screened for red cell alloimmunisation at 27 weeks gestation. We expect a 80% enrolment, based on our experience during the OPZI-study.[13] Therefore our sample size will consist of approximately 240 new cases of HPA-1a alloimmunisation, with at least 7 and more likely 10 neonates suffering from ICH.

However, the numbers above are based on published cohorts that did not describe the natural history of HPA-1a-mediated FNAIT.[1] Identified cases of FNAIT were treated with various modalities; therefore, the true prevalence would likely be higher. A second systematic review, using data from postnatal screening studies, confirmed that attempts to assess the prevalence of neonatal FNAIT purely based on clinical evaluation of symptomatic bleeding leads to significant underestimation of the prevalence.[14] Many cases had been missed. We therefore expect to find an even higher incidence of FNAIT with adverse perinatal outcomes, possibly between 1 in 5.000 and 1 in 10.000 pregnancies. Obviously, solid estimates of these numbers are essential elements for the development and implementation of a national HPA-screening program.

**5. TREATMENT OF SUBJECTS**

*Not applicable*

**6. INVESTIGATIONAL PRODUCT**

*Not applicable*

**7. NON-INVESTIGATIONAL PRODUCT**

*Not applicable*

## 8. METHODS

### 8.1 Study parameters/endpoints

#### 8.1.1 Main study parameter/endpoint

The main study parameter is the incidence of HPA-1a alloantibodies and the incidence of clinically relevant FNAIT. Clinically relevant FNAIT will be defined as perinatal death, ICH or internal organ haemorrhage.

#### 8.1.2 Secondary study parameters/endpoints

- Laboratory platform for antibody screening and assay(s) for identification of cases, who need treatment.
- Neonatal outcome:
  - Laboratory findings: platelet count, haemoglobin, CRP, other
  - Neonatal bleeding signs other than ICH or internal organ haemorrhages: petechiae, hematoma, purpura, mucosal bleeding, other.
  - Neonatal treatment of thrombocytopenia: platelet transfusion (random versus matched), IvIG, red blood cell transfusion, other.
  - Neonatal morbidity: infections, hours/days in hospital (NICU versus Medium Care), need for additional treatments, congenital abnormalities, other causes causing increased bleeding tendency.

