#### *Statistical analysis*

For comparison of the secondary study parameters to a control group we will be using the HPA-1a negative women without the formation of alloantibodies as well as HPA-1a positive cases. For categorical variables we will be using Pearson’s chi-square tests and Fisher’s exact tests when applicable and for continuous variables we will be using Student’s t-test or Mann-Whitney test, as appropriate.

We expect perinatal death or ICH due to FNAIT to be the most infrequent outcome. As described before we expect a total of 10 cases of ICH in our study population. In the controls we expect 0-1 ICH will develop. This will lead to a significant difference between the study group and the controls (P<0.0001).

	Case (As+)	Control (As-)	
ICH +	10 (a)	1 (c)	11
ICH-	110 (b)	359 (d)	469
	120	360	480

*Relative risk:  $a/(a+b)/c/(c+d) = (10/120)/(1/360) = 0,0833/0,00278=30$*

*Fisher exact test:  $p < 0.0001$*

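### Neonates treated for thrombocytopenia without a major bleed are classed low-risk, so assay PPV and the benefit count may be too low by an amount the plan should bound

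*Protocol*

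**What the plan says.** - Protocol 8.1.1 fixes the target condition: "Clinically relevant FNAIT will be defined as perinatal death, ICH or internal organ haemorrhage". It has no platelet-count or treatment component.
- Protocol section 3 fixes the two classes for the experimental assays, which are to "discriminate high risk cases, who will develop clinically relevant disease, from low-risk cases".
- Protocol 8.1.2 lists "Neonatal treatment of thrombocytopenia: platelet transfusion (random versus matched), IvIG, red blood cell transfusion, other" among the secondary neonatal outcomes, next to platelet count. Section 10.2 gives these variables a group comparison and nothing more: "For categorical variables we will be using Pearson’s chi-square tests and Fisher’s exact tests when applicable".
- A secondary objective in section 2 is "To determine the number of pregnant women whose children would benefit from treatment and the number who will receive treatment unnecessarily". Neither count is defined.
- Section 1 presents the work as a "prospective study providing information about the natural course of this disease".
- Section 4.4 explains why earlier cohorts understate the disease: "Identified cases of FNAIT were treated with various modalities; therefore, the true prevalence would likely be higher".
- The Summary raises overtreatment with a different yardstick in view: "approximately 10-30% of the HPA alloimmunised cases result in severe thrombocytopenia and clinically relevant disease".

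**The concern.** Neonatal treatment comes after the 27-week sample on which the assays are run and can come before the outcome that defines high risk. Take a neonate of an antibody-positive mother with a platelet count below 50 x10⁹/L who is given platelets or IvIG and has no death, ICH or organ haemorrhage. Sections 3 and 8.1.1 together make this pregnancy low-risk, and an assay that flagged it was wrong. If treatment prevented the bleed, the assay was right.

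Section 4.4 uses this argument against published cohorts, but no section applies it to the study's own data. Affected are the PPV of the assays, the two counts in the secondary objective, and the description of the incidence as natural course. With about 8 expected ICH cases, a few reclassified pregnancies matter. Treated neonates without an event are also where the two possible yardsticks, major bleeding and severe thrombocytopenia, give opposite answers.

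**Working it through.** **Inputs, all from Protocol 4.4:** 60,000 eligible women a year, 2 years, 80% enrolment, 2.1% HPA-1a negative, 12% alloimmunised, one third of these severe (platelets <50 x10⁹/L), 10% of severe cases with ICH.

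**The plan's own figures**
- Enrolled: 60,000 x 2 x 0.80 = 96,000
- Antibody-positive: 96,000 x 0.021 x 0.12 = 241.9 (stated: about 240)
- Severe: 241.9 / 3 = 80.6
- ICH: 80.6 x 0.10 = 8.1. The quoted rate of 1:12,500 gives 96,000 / 12,500 = 7.7. Both agree with the stated minimum of 7; the stated 10 needs a rate near 1:10,000 (9.6).

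**Severe neonates who enter the low-risk class**
- 80.6 - 8.1 = 72.6, out of 241.9 - 8.1 = 233.9 low-risk pregnancies (31%).
- At the 10% severe fraction in the Summary, with ICH held at 8: 24 - 8 = 16, out of 232 (7%).
- These counts use ICH alone, because section 4.4 gives no rates for death or organ haemorrhage. They are therefore slightly high.

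**Masked events.** Two quantities are needed that the documents do not give. I assume that 10-75% of the 72.6 are treated, and that 0-10% of those treated would otherwise have had a major bleed.
- Treated: 72.6 x 0.10 = 7 to 72.6 x 0.75 = 54
- Masked: 0 to 72.6 x 0.75 x 0.10 = 5.4, against about 8.1 observed
- Largest under-count of events: 5.4 / (8.1 + 5.4) = 40%

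**Effect on an assay that flags exactly the severe cases**

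| | As classified | Largest masking (5.4) |
|---|---|---|
| PPV | 8.1/80.6 = 10% | 13.5/80.6 = 17% |
| Specificity | 161.3/233.9 = 69.0% | 161.3/228.4 = 70.6% |

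The assay leaves 241.9 - 80.6 = 161.3 pregnancies unflagged. PPV shifts noticeably and specificity hardly at all. A second illustration points the same way. It assumes 240 antibody-positive pregnancies, 8 observed events, 90% sensitivity and 80% specificity. With 3.6 masked events (72 x 0.50 x 0.10), apparent specificity is 0.789 against 0.80, PPV is 0.13 against 0.19, and apparent unnecessary treatments are 49 against 46.

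**Counting every treated no-event neonate as high-risk.** PPV of the first assay would be (8.1 + 7.3)/80.6 = 19% to (8.1 + 54.4)/80.6 = 77.5%. This changes the target condition. It is an outer bound and not an estimate of the bias.

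**The case against.** The strongest reply is that the design already limits masking. Section 11.4 withholds the typing result and places antibody testing after birth. Section 8.3 puts that testing more than two weeks after the due date and keeps the screening result from caregivers. Only ordinary clinical recognition can lead to neonatal treatment, and section 1 says that in current practice treatment often comes too late. Section 1 also reports ICH of antenatal origin, which treatment after birth cannot avert. Masking may therefore be close to zero. This stands as a limit on size. It does not remove the problem, because section 8.3 provides for clinically suspected cases and 8.1.2 expects some neonates to be treated.

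A second reply is that section 4.4 speaks of various treatments, and section 1 names antenatal treatment and selected populations as the fault in the literature. That is fair: section 4.4 does not single out postnatal care. It still accepts that treatment lowers observed prevalence.

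A third reply is that handling of treatment given after the index test belongs in a SAP, which is not shown. This holds for sensitivity analyses. The endpoint and the two classes, however, are fixed in the protocol.

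**Conclusion.** The point holds in a limited form. Sections 3 and 8.1.1 class treated neonates without a major bleed as low-risk, and nothing connects the treatment data to assay accuracy, to the benefit and unnecessary-treatment counts, or to the natural-course wording. PPV and the would-benefit count may be too low and the unnecessary count too high, with little effect on specificity. Under the assumed ranges, 0 to about 5 events are masked against about 8 observed, and PPV in the worked example goes from 10% to at most about 17%. The treated and averted shares are assumptions, so the true effect may be nil.

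Stronger readings that the documents do not support:
- A reader might infer that the plan counts these women as treated unnecessarily. Section 2 defines neither count, and the Summary and section 1 discuss overtreatment by reference to severe thrombocytopenia. It is a possible reading and not the text.
- A reader might take the 7 to 54 treated neonates as misclassified. Only those who would otherwise have had a major bleed are.
- A reader might say that these neonates do not bleed. They may have petechiae, haematoma, purpura or mucosal bleeding, which lie outside the endpoint.
- A reader might conclude that they should be left out of the accuracy analysis. That selects on treatment and outcome together. If 75% were treated and treatment averted nothing, the true PPV would stay at 10% while the analysis without them gave 8.1/(80.6 - 54.4) = 31%.

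**What to change.** 1. Keep the 8.1.1 endpoint and the section 3 classification as the main analysis, and do not exclude treated no-event neonates from it.
2. Report neonates of antibody-positive mothers who received platelet transfusion or IvIG for thrombocytopenia and had no event as a separate category, from the data listed in 8.1.2.
3. Give assay accuracy and the two section 2 counts twice, with this category as low-risk and as high-risk, and label the results as bounds.
4. State which yardstick, major bleeding or severe thrombocytopenia, defines benefit and unnecessary treatment in section 2.
5. Describe the 8.1.1 incidence as incidence without treatment triggered by screening, under current neonatal care, and not as untreated natural course.

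The cost is wording and some extra tabulation. No new data, samples or procedures are needed. The downside is a range instead of a single figure, and the range could be wide if many neonates were treated.
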